			0:05	08:05				x			
			0:10	08:10				x			
			0:15	08:15				x			
			0:20	08:20				x			
			0:25	08:25				x	x ⁸		
			0:30	08:30	End of infusion		▼	x			x
			0:32	08:32				x			
			0:34	08:34				x			
			0:36	08:36				x			
			0:40	08:40				x			
			0:45	08:45				x			
			0:50	08:50				x			
			1:00	09:00	240 mL fluid intake			x	x ^{8,9}		x
			1:20	09:20				x			
			1:40	09:40				x			
			2:00	10:00	Snack , 240 mL fluid intake			x	x ⁸		x
			3:00	11:00	Assessment of local tolerability			x			x
			4:00	12:00	lunch ³	B		x		x	x
			6:00	14:00				x			x
			7:30	15:30	Snack						
			10:45	18:45	Assessment of local tolerability ¹⁰ (all subjects together)	x ⁷					x ¹⁰
			11:00	19:00	Dinner						
	3	1	-1:30	06:30				x ²	x ^{2,8}	x ²	x ²
			-0:15	07:45		B		x	x ^{8,9}		
			-0:05	07:55	i.v.-bolus of standard heparin						
			0:00	08:00	Start of alteplase infusion		▲				
			0:05	08:05				x			
			0:10	08:10				x			
			0:15	08:15				x			
			0:20	08:20				x			
			0:25	08:25				x	x ⁸		
			0:30	08:30	End of infusion		▼	x			x
			0:32	08:32				x			
			0:34	08:34				x			
			0:36	08:36				x			
			0:40	08:40				x			
			0:45	08:45				x			
			0:50	08:50				x			

Treatments periods will be performed on 2 consecutive days

Proprietary confidential information © 2021 Boehringer Ingelheim International GmbH or one or more of its affiliated companies

			1:00	09:00	240 mL fluid intake			x	x ^{8,9}		x
			1:20	09:20				x			

Period	Visit	Day	Planned time (relative to start of infusion [h:min])	Approximate clock time of actual day [h:min]	Event and comment	Safety laboratory	Alteplase Infusion	PK _{blood} (x) / ADA (y)	Biomarkers ⁸	Vital signs (BP, PR)	Questioning for AEs and concomitant therapy ⁶
3	1	1	1:40	09:40				x			
			2:00	10:00	Snack, 240 mL fluid intake			x	x ⁸		x
			3:00	11:00	Assessment of local tolerability			x			x
			4:00	12:00	lunch ³	B		x		x	x
			6:00	14:00				x			x
			7:30	15:30	Snack						
			10:45	18:45	Assessment of local tolerability ¹⁰ (all subjects at that time)						x ¹⁰
			11:00	19:00	Dinner						
		2	24:00	08:00	Assessment of local tolerability, Breakfast (voluntary), discharge from trial site	B		x ⁸	x	x	
EOT	4		8-22		End of trial (EOT) examination ⁴	C			x	x	

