5.2.3 Safety laboratory parameters

For the assessment of laboratory parameters, blood and urine samples will be collected by the trial site at the times indicated in the [Flow Chart](#).

The parameters that will be determined are listed in Tables [5.2.3: 1](#) and [5.2.3: 2](#). Reference ranges will be provided in the ISF, Section 10.

Manual differential white blood cell count or urine sediment examinations will only be performed if there is an abnormality in the automatic blood cell count or in the urinalysis, respectively.

Fecal occult blood testing, using an immunochemical test kit for hemoglobin (e.g. BioNexia® FOBplus, [REDACTED]), will be performed at the trial site.

Proprietary confidential information © 2021 Boehringer Ingelheim International GmbH or one or more of its affiliated companies

Table 5.2.3: 1

Routine laboratory tests

Functional lab group	BI test name [comment/abbreviation]	A ¹	B ¹		C ¹
Haematology	Haematocrit	X	X	-	X
	Haemoglobin	X	X	-	X
	Red Blood Cell Count/Erythrocytes	X	X	-	X
	White Blood Cells/Leucocytes	X	X	-	X
	Platelet Count/Thrombocytes (quant)	X	X	-	X
Automatic WBC differential, relative	Neutrophils/Leukocytes; Eosinophils/Leukocytes; Basophils/Leukocytes; Monocytes/Leukocytes; Lymphocytes/Leukocytes	X	-	-	X
Automatic WBC differential, absolute	Neutrophil, absol.; Eosinophils, absol.; Basophils, absol.; Monocytes, absol.; Lymphocytes, absol.	X	-	-	X
Manual differential WBC (if automatic differential WBC is abnormal)	Neut. Poly (segs); Neut. Poly (segs), absol.; Neutrophils Bands; Neutrophils Bands, absol.; Eosinophils/Leukocytes; Eosinophils, absol.; Basophils/ Leukocytes; Basophils, absol.; Monocytes/ Leukocytes; Monocytes, absol.; Lymphocytes/Leukocytes; Lymphocytes, absol.				
Coagulation	Activated Partial Thromboplastin Time	X	X		X
	Prothrombin time – INR (International Normalization Ratio)	X	X		X
	Fibrinogen	X	X		X
	Antithrombin III	X			
	Protein C	X			
Enzymes	Protein S	X			
	Activated protein C resistance	X			
	AST [Aspartate transaminase] /GOT, SGOT	X	-	-	X
	ALT [Alanine transaminase] /GPT, SGPT	X	-	-	X
	Alkaline Phosphatase	X	-	-	X
Hormones	Gamma-Glutamyl Transferase	X	-	-	X
	Amylase	X	-	-	-
	Lipase	X	-	-	-
	Thyroid Stimulating Hormone	X	-	-	-
Substrates	Glucose (Plasma)	X	-	-	X
	Creatinine	X	-	-	X
	Bilirubin, Total	X	-	-	X
	Bilirubin, Direct	X	-	-	X
	Protein, Total	X	-	-	X
	C-Reactive Protein (Quant)	X	-	-	X
Electrolytes	Sodium	X	-	-	X
	Potassium	X	-	-	X
	Calcium	X	-	-	X

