7.3.4 Safety analyses

Safety will be analysed based on the assessments described in Section [2.2.2.2](#). All treated subjects (TS, refer to Section [7.2](#)) will be included in the safety analysis. Safety analyses will be descriptive in nature and based on BI standards. No hypothesis testing is planned.

For all analyses, the treatment actually administered (= treatment at onset) to the subject will be used (any deviations from the randomised treatment will be discussed in the minutes of the Report Planning Meeting).

Treatments will be compared in a descriptive way. Tabulations of frequencies/proportions will be used to evaluate categorical (qualitative) data, and tabulations of descriptive statistics will be used to analyse continuous (quantitative) data.

Measurements (such as ECG, vital signs, or laboratory parameters) or AEs will be assigned to treatments (see Section [4.1](#)) based on the actual treatment at the planned time of the measurement or on the recorded time of AE onset (concept of treatment emergent AEs).

Therefore, measurements planned or AEs recorded prior to first intake of trial medication will be assigned to the screening period, those between first trial medication intake and end of REP (see Section [1.2.3](#)) will be assigned to the treatment period. Events occurring after the REP but prior to next intake or end of trial termination date will be assigned to 'follow-up'. In case of two or more treatments, the follow-up will be summarized according to the previous treatment. These assignments including the corresponding time intervals will be defined in detail in the Trial statistical analysis plan (TSAP). Note that AEs occurring after the last per protocol contact but entered before final database lock will be reported to Pharmacovigilance only and will not be captured in the trial database.

Additionally, further treatment intervals (analysing treatments) may be defined in the TSAP in order to provide summary statistics for time intervals, such as combined treatments, on-treatment totals, or periods without treatment effects (such as screening and follow-up intervals).

Adverse events will be coded using the Medical Dictionary for Regulatory Activities (MedDRA). Frequency, severity, and causal relationship of AEs will be tabulated by treatment, system organ class, and preferred term. SAEs, AESIs (see Section [5.2.6.1](#)), and other significant AEs (according to ICH E3) will be listed separately.

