6. GENERAL ANALYSIS DEFINITIONS

6.1 TREATMENTS

For basic study information on treatments to be administered, assignment of treatment groups, and selection of doses, cf. Section 4 of the CTP.

All subjects will receive the 2 treatments (TPA-02 and TPA-05) in randomised order at 2 consecutive days. The specific alteplase dose to be administered to a given subject will be calculated based on the body weight measured at screening examination. Prior to the first administration of trial medication, subjects will be assigned to treatment sequences T-R or R-T.

For statistical analysis of AEs, safety laboratory data, vital signs and ECG, the following analysis phases are defined for each subject:

Table 6.1: 1 Flow chart of analysis phases for statistical analyses of AEs, safety laboratory and vital signs

Study analysis phase	Label	Start (inclusive)	End (exclusive)
Screening	Screening	Date of informed consent	Date/time of first administration of TPA-02/ TPA-05
On-treatment	TPA-02 0.2 mg/kg body weight	Date/time of first administration of TPA-02	Date/time of first administration of TPA-05 or 12:00 a.m. on day after subject's trial termination date, whichever occurs earlier
On-treatment	TPA-05 0.2 mg/kg body weight	Date/time of first administration of TPA-05	Date/time of first administration of TPA-02 or 12:00 a.m. on day after subject's trial termination date, whichever occurs earlier

Analysis phases for statistical analysis of AEs are defined for each subject as described in the table above.

CTR Section 15, Appendix 16.1.13.1.8.2 and Appendix 16.1.13.1.8.3 AE displays will present results for the on-treatment phase and screening phase.

In CTR Section 15 AE tables (but not in Appendix 16.1.13.1.8.2 and Appendix 16.1.13.1.8.3 AE tables), the following totals will be provided in addition:

- **"Total on-trt"**, defined as the total over all on-treatment phases involving BI

Safety laboratory data and vital signs will be analysed by treatment (TPA-02 or TPA-05).

More details on the technical implementation of these analyses are provided in the ADS Plan of this TSAP.

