7.8.1 Adverses Events

AEs will be coded with the most recent version of MedDRA. The Residual Effect Period (REP) of alteplase is 24 hours (i.e. 23.5h after end of infusion) in this trial, see CTP Section 1.2.3.

The analyses of AEs will be descriptive in nature. All analyses of AEs will be based on the number of subjects with AEs and not on the number of AEs.

For further details on summarization of AE data, please refer to "Analysis and Presentation of Adverse Event Data from Clinical Trials" (7) and "Handling of missing and incomplete AE dates" (3).

The analysis of AEs will be based on the concept of treatment emergent AEs. That means that all AEs will be assigned to screening or on-treatment phases as defined in [Section 6.1](#). AEs will be analysed based on actual treatments, as defined in [Table 6.1: 1](#).

An overall summary of AEs will be presented. This overall summary will comprise summary statistics for the class of other significant AEs according to ICH E3 (8) and for the class of AESIs.

CTP Section 5.2.6.1.4: *The following are considered as AESIs:*

- *Hepatic injury*
A hepatic injury is defined by the following alterations of hepatic laboratory parameters:
 - *An elevation of AST (aspartate transaminase) and/or ALT (alanine transaminase) ≥ 3 -fold ULN combined with an elevation of total bilirubin ≥ 2 -fold ULN measured in the same blood sample, or*

- *Aminotransferase (ALT, and/or AST) elevations ≥ 10 fold ULN*

The investigator had to classify on the eCRF whether an observed AE was an AESI or not.

According to ICH E3 (8) AEs classified as "other significant" need to be reported and will include those non-serious and non-significant AEs

- (i) which are marked haematological or other lab abnormalities, or
- (ii) which were reported with "action taken = discontinuation" or "action taken = reduced", or
- (iii) which lead to significant concomitant therapy as identified by the Clinical Monitor/Investigator at a Medical Quality Review Meeting.

The frequency of subjects with AEs will be summarised by treatment, primary SOC and preferred term. AEs which were considered by the investigator to be drug related will be summarised separately. Separate tables will also be provided for subjects with SAEs, subjects with AESIs and subjects with other significant AEs (according to ICH E3 (8)). AEs will also be summarized by maximum intensity.

The SOCs and preferred terms within SOCs will be sorted by descending frequency over all treatment groups.

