For disclosure of AE data typically intended for ClinicalTrials.gov, the frequency of subjects with non-serious AEs occurring with an incidence of greater than 5 % (in preferred terms) will be summarised by treatment, primary SOC and preferred term. The frequency of subjects with SAEs will also be summarised.

For disclosure of AE data in the EudraCT register, the frequency of AEs, the frequency of non-serious AEs with an incidence of greater than 5 % (in preferred terms) and the frequency of SAEs will be summarized.

For support of lay summaries, the frequency of subjects with drug-related SAEs will be summarized by treatment, primary SOC and preferred term.

7.8.2 **Laboratory data**

The analyses of laboratory data will be descriptive in nature and will be based on BI standards "Display and Analysis of Laboratory Data" (9).

Analyses will be based on normalised values, which mean transforming to a standard unit and a standard reference range. The original values will be analysed if the transformation into standard unit is not possible for a parameter.

Descriptive statistics of absolute values and change from baseline from laboratory parameters over time (see [Section 6.7](#)) will be provided. Frequency tables of changes between baseline and last value on treatment with respect to the reference range will be presented.

Individual line plots as well as plots on aggregated data presenting median with Q1 and Q3 as error bars will be provided for plasminogen and α 2-antiplasmin.

Unscheduled measurements of laboratory data will be assumed to be repeat measurements of the most recent scheduled measurement (e.g. for follow-up or confirmation of a particular value). Therefore, unscheduled measurements will be assigned to the planned time point of the previous scheduled measurement. Descriptive statistics will be calculated by planned time point based on the worst value of the subject at that planned time point (or assigned to that planned time point).

Possibly clinically significant abnormal laboratory values are only those identified either in the Investigator's comments or at the RPM at the latest. It is the Investigator's responsibility to decide whether a lab value is clinically significant abnormal or not. Standard or project-specific rules for flagging clinically significant values in an automated manner will not be applied in this study.

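### SAP Table 6.1:1 folds the protocol's post-REP follow-up into on-treatment without declaring it, and its phase-end rule fails for the product given second

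*SAP*

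**What the plan says.** Protocol 7.3.4 sets three categories. Data before the first dose belong to screening. Data from first intake to the end of the REP belong to the treatment period. For what comes later it says: "Events occurring after the REP but prior to next intake or end of trial termination date will be assigned to" follow-up, and with two or more treatments "the follow-up will be summarized according to the previous treatment". It leaves the detailed definition of these assignments and their intervals to the SAP. Protocol 1.2.6 sets the REP at 24 h.

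SAP Table 6.1:1 has a screening row and one on-treatment row per product. The TPA-05 row ends at "Date/time of first administration of TPA-02 or 12:00 a.m. on day after" the subject's trial termination date, whichever is earlier; the TPA-02 row mirrors it. SAP 6.1 adds that "AE displays will present results for the on-treatment phase and screening phase". SAP 7.8.1 restates the 24 h REP, yet says that "all AEs will be assigned to screening or on-treatment phases". The SAP 6.1 phases also govern laboratory data, vital signs and ECG, and for laboratory data SAP 7.8.2 plans: "Frequency tables of changes between baseline and last value on treatment with respect to the reference range will be presented". SAP 4 states full accordance with the protocol.

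**The concern.** There are two defects, and they bite under different readings of the table.

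- **A named phase is missing.** The SAP quotes the REP but no phase boundary uses it. If the end rule means the next administration, everything after the last infusion, including the end-of-trial (EOT) visit, is on-treatment for the second product.
- **The end rule is misdrafted.** It refers to the first administration of the other product. For whichever product is given second, that moment has already passed. Read literally, a completer's second-period and EOT data fall in no phase.

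At stake are the AE tables, the 'Total on-trt' column and the laboratory shift tables. An AE arising two weeks after the last infusion would be reported as on-treatment. So would a hepatic injury, the only listed AE of special interest, if first detected by the scheduled EOT chemistry.

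**Working it through.** **Inputs**

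- REP: 24 h (Protocol 1.2.6). SAP 7.8.1 restates it as 23.5 h after the end of infusion. Check: 24 − 0.5 h infusion = 23.5 h, which reproduces.
- Infusions: about 08:00 on two consecutive days (Protocol Flow Chart).
- EOT visit: Day 8 to 22 (Flow Chart), counted here from the second infusion day. This fits Protocol 6.2.3, which puts EOT at least one week after the last dose. Trial termination is taken as the EOT date.

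**Literal reading, sequence R-T.** The TPA-05 phase starts at the second infusion and ends at the earlier of the first TPA-02 administration (24 h before) and trial termination. Its length is −24 h, so it is empty. TPA-02 in sequence T-R behaves identically.

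**'Next administration' reading, completer**

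| Quantity | EOT Day 8 | EOT Day 22 |
|---|---|---|
| First-product phase | 24 h | 24 h |
| Second-product phase (Day × 24 − 8) | 8 × 24 − 8 = 184 h | 22 × 24 − 8 = 520 h |
| Second phase relative to the REP | 184/24 = 7.7 | 520/24 = 21.7 |
| Total on-treatment time | 208 h | 544 h |
| Share beyond two 24 h REPs | (208 − 48)/208 = 76.9% | (544 − 48)/544 = 91.2% |

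If EOT days were counted from the first infusion instead, total time would be 184 to 520 h. The share would be (184 − 48)/184 = 73.9% to (520 − 48)/520 = 90.8%, so the conclusion does not depend on the anchor.

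**Laboratory values.** In Protocol Table 5.2.3:1, rows such as "ALT [Alanine transaminase] /GPT, SGPT" are marked for profile A (screening) and profile C (EOT) but not profile B (treatment days). The chemistry rows with this pattern are:

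- 4 enzymes: AST, ALT, alkaline phosphatase, gamma-GT
- 6 substrates: glucose, creatinine, total and direct bilirubin, total protein, C-reactive protein
- 3 electrolytes: sodium, potassium, calcium

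That makes 4 + 6 + 3 = 13. Their only scheduled post-dose value is the EOT value. The second REP ends at about 08:00 on Day 2, so that value is taken 8 − 2 = 6 to 22 − 2 = 20 days later. For a completer it is the last value on treatment in the SAP 7.8.2 shift table, always for the second product.

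**The case against.** The strongest reply is that this is an alignment slip in descriptive output.

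- **Delegation.** Protocol 7.3.4 leaves the intervals to the SAP and allows further ones, such as combined treatments. That permits detail and additions. It does not clearly permit removing a named category while SAP 4 claims full accordance.
- **One sensible implementation.** Each product is given once, so a programmer would read 'next', and SAP 6.1 refers to an ADS Plan that was not available for this review. This is fair for the wording defect, but a technical plan should not have to repair an SAP definition that contradicts itself. It does nothing for the missing phase.
- **Attribution is unchanged.** Correct: the protocol also summarises follow-up under the previous treatment. With infusions 24 h apart and a 24 h REP, there is almost no follow-up between periods. What changes is the on-treatment versus follow-up split after the last dose.
- **Other laboratory tables.** SAP 7.8.2 also gives statistics by planned time point, and SAP 7 lists individual values, so EOT values stay identifiable there. The shift tables, AE tables and 'Total on-trt' remain affected.
- **Events versus measurements.** The protocol's follow-up sentence speaks only of events. EOT laboratory values are clearly outside its treatment period; placing them in follow-up is an inference, though the natural one.
- **Unknown impact.** The percentages are shares of time. The documents give no post-REP AE rate, so the number of reclassified events cannot be stated.

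**Conclusion.** The concern holds. The SAP drops the protocol's follow-up phase without declaring it, and its end rule is wrong as written for the product given second. On the 'next administration' reading, with 08:00 dosing and EOT on Day 8 to 22 after the second infusion, the second on-treatment phase lasts 184 to 520 h against a 24 h REP. About 77% to 91% of a completer's total on-treatment time lies beyond the two REPs. For 13 chemistry parameters, every scheduled post-dose value is labelled on-treatment although the protocol's treatment period has ended.

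Safety analysis is descriptive, product labels stay correct, and 1:1 sequences mean that neither product is expected to be favoured. The bioequivalence test is not touched. The correction should be made before the safety tables are programmed.

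**What to change.** 1. In SAP Table 6.1:1, end each on-treatment phase at the earliest of the next alteplase infusion after the phase start, the end of the 24 h REP, or midnight after the trial termination date. The Flow Chart's 24:00 row ("Assessment of local tolerability, Breakfast (voluntary), discharge from trial site") sits exactly on that boundary. State that its laboratory and vital-sign measurements after the second infusion count as on-treatment by planned time point.
2. Add a follow-up row from the end of the REP to the next infusion or trial termination, summarised under the preceding treatment.
3. In SAP 7.8.1 and in the AE-display sentence of SAP 6.1, name screening, on-treatment and follow-up, so that post-REP AEs and hepatic events found at EOT stay in the tables.
4. In SAP 7.8.2, present baseline-to-EOT shifts, labelled follow-up, for parameters whose only scheduled post-dose measurement is in profile C. Without this, the 13 chemistry parameters would have no scheduled value for the shift table.

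Alternatively, declare and justify in SAP 4 that follow-up is merged into on-treatment, and still change the end rule to the next administration.

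The cost is SAP text, the dataset specification and one extra phase in the AE and laboratory table shells. Data collection does not change.

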6.2 IMPORTANT PROTOCOL DEVIATIONS

Consistency check listings (for identification of deviations from time windows) and a list of protocol deviations (e.g. deviations in drug administration, in blood sampling times, etc.) will be provided to be discussed at the Report Planning Meeting for the final analysis. At this meeting, it will be decided whether a discrepant data value can be used in analyses or whether it must be corrected in the clinical database. Each protocol deviation must be assessed to determine whether it is an important protocol deviation (IPD). For definition of IPDs, and for the process of identification of these, refer to the BI reference document "Identify and Manage Important Protocol Deviations (IPD)" (2).

For the interim analysis a meeting to discuss deviations related to PK will be conducted and the decisions will be documented in a decision log.

If any IPDs are identified, they are to be summarised into categories and will be captured in the decision log. Categories which are considered to be IPDs in this trial are defined in the integrated quality and risk management plan (IQRMP).

IPDs will be summarized and listed. [Table 6.2: 1](#) below specifies which kind of IPDs could potentially lead to exclusion from which analysis set. The decision on exclusion of subjects from analysis sets will be made at the latest at the Report Planning Meeting, after discussion of exceptional cases and implications for analyses. If the data show other IPDs, this table will be supplemented accordingly by the time of the Report Planning Meeting.

Table 6.2: 1 Handling of iPDS

iPD code	iPD Category & Brief Description	Excluded from which analysis set
A1	Inclusion Criteria violated	PKS
A2	Exclusion Criteria violated	PKS
B1	Informed consent not available/not done	TS, PKS
B2	Informed consent too late	None
C1	Incorrect trial medication intake	PKS
C2	Randomisation not followed	PKS
C3	Non-compliance	PKS
C4	Medication code broken inappropriately	PKS
C5	Incorrect intake of trial medication	PKS
C6	Improper washout between treatments	PKS
D1	Prohibited medication use	PKS
D2	Mandatory medication not taken	PKS
D3	Improper washout of concomitant medication	PKS
E1	Certain violations of procedures used to measure primary or secondary data	PKS
F1	Certain violations of time schedule used to measure primary or secondary data	PKS
G1	Incorrect intake of meal	PKS

